### 2.6.2 Statistical hypothesis, model, and method of analysis

It will be analyzed using the same MMRM (including all available visits) on the FAS as used for the primary analysis but will include Baseline ACQ-7 score instead of Baseline FEV1.

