#### 2.6.4 Multiplicity adjustment

A hierarchical testing procedure will be applied to control the type-I error rate for the primary and the key secondary endpoints, i.e., the key secondary endpoint ACQ-7 will be tested only if the primary endpoint (trough FEV1) is significant at the 2-sided 0.05 level.

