## **2.7.2 Asthma control questionnaire (ACQ)**

Results for ACQ-7 at day 30, obtained from MMRM for the key secondary endpoint ACQ-7 at day 84, will be displayed.

Change from baseline in the ACQ-7 will be also analyzed using the same MMRM model.

The proportion of patients who achieve an improvement of at least 0.5 in ACQ-7 (i.e. decrease of ACQ-7 score of at least 0.5 from Baseline) at post-baseline visits will be analyzed using a logistic regression model. First missing ACQ-7 values will be imputed using a regression based Multiple Imputation (MI) method under missing at random (MAR) assumption, based on continuous ACQ values. Then continuous ACQ values will be converted into binomial responses and generalized estimating equation (GEE) method will be used to analyze the datasets and then the results from GEE method will be combined for the inference. The GEE model will include terms for treatment, age (12 to 17 or  $\geq 18$  years), region, visit, and treatment-by-visit interaction as fixed effects, and Baseline ACQ-7, Baseline-by-visit interaction, FEV1 prior to inhalation and FEV1 within 15 to 30 min post inhalation of salbutamol/albuterol (components of SABA reversibility) as covariates. The estimated adjusted odds ratio will be displayed along with the associated 95% (2 -sided) confidence interval and p-value.

Additionally, the number of patients will be summarized by response relative to baseline ACQ-7 with the following categories: Response (decrease of  $\geq 0.5$  units in ACQ-7), No change ( $-0.5 < \text{change in ACQ-7} < 0.5$ ), Worsening (increase of  $\geq 0.5$  units in ACQ-7), Net response (response – worsening) and Total.

In addition to ACQ-7, average of first 5 questions in ACQ (ACQ-5) will be calculated and all the analyses described for ACQ-7 will be repeated for ACQ-5.

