The endpoint is assumed to have a normal distribution at Day 2 and Week 12. The primary analysis is performed on the delta-adjusted datasets to see if the conclusions change. If not, a larger delta is chosen and the process is repeated until the conclusion is overturned. The tipping point is the delta value which will cause the QMF149 vs. MF comparison on the primary endpoint to be no longer statistically significant. A series of analyses on a range of delta values will be performed to find the tipping point. For each delta value, the following steps will be performed.

1. Impute missing covariates (baseline FEV1, FEV1 prior to inhalation and FEV1 15 to 30 min post inhalation value) and missing values at Day 2 and/or Week 12 using the MI approach based on the fully conditional specification (FCS) method for 100 times and obtain 100 imputed datasets. Missing baseline FEV1, FEV1 prior to inhalation and FEV1 15 to 30 min post inhalation value will be imputed separately for each treatment group using a model with age group, geographic region, and the respective other covariates (baseline FEV1, FEV1 prior to inhalation and FEV1 15 to 30 min post inhalation value) as predictors. Missing Day 2 values will be imputed separately for each treatment group using a model with the imputed values of age group, geographic region, baseline FEV1, FEV1 prior to inhalation and FEV1 15 to 30 min post inhalation value as predictors. Missing Week 12 values will be imputed separately for each treatment group using a model with the imputed values of age group, geographic region, baseline FEV1, FEV1 prior to inhalation, FEV1 15 to 30 min post inhalation, and Day 2 value as predictors.
2. After the imputation obtained in above step, for subjects in the QMF149 treatment arms only, make the imputed value at Week 12 worse by a value of delta (i.e., subtract delta from the imputed value at Week 12). Note: delta = 0 represents the standard missing at random (MAR) based MI.
3. The final multiply-imputed dataset where all missing values are filled will be analyzed (by imputed dataset) using a linear mixed model with treatment, age group, geographic region, baseline FEV1, FEV1 prior to inhalation, and FEV1 within 15 to 30 min post inhalation as predictors.

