4. The results for the treatment effect from the 100 datasets will then be combined using Rubin's rule. If the combined results does not change the conclusion (i.e., the QMF149 treatment effect is still statistically significantly superior to MF), a larger delta will be chosen and Steps 1-4 will be repeated using the datasets from Step 2 until the tipping point is found (when  $p > 0.05$ ).

- **Logistic regression analysis**

The analysis of proportion of patients who achieve an improvement of at least 0.5 in ACQ-7 (i.e. decrease of ACQ-7 score of at least 0.5 from Baseline) at post-baseline visits will be performed using the following steps:

1. Impute missing covariates (baseline ACQ-7, FEV1 prior to inhalation and FEV1 15 to 30 min post inhalation value) and missing continuous ACQ-7 values at Day 30 and/or Week 12 using the MI approach based on the fully conditional specification (FCS) method for 100 times and obtain 100 imputed datasets. Missing baseline ACQ-7, FEV1 prior to inhalation and FEV1 15 to 30 min post inhalation value will be imputed separately for each treatment group using a model with age group, geographic region, and the respective other covariates (baseline ACQ-7, FEV1 prior to inhalation and FEV1 15 to 30 min post inhalation value) as predictors. Missing Day 30 values will be imputed separately for each treatment group using a model with the imputed values of age group, geographic region, baseline ACQ-7, FEV1 prior to inhalation and FEV1 15 to 30 min

post inhalation value as predictors. Missing Week 12 values will be imputed separately for each treatment group using a model with the imputed values of age group, geographic region, baseline FEV1, FEV1 prior to inhalation, FEV1 15 to 30 min post inhalation, and Day 30 value as predictors.

The SAS procedure PROC MI will be used and this will result in 100 copies of the original dataset.

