2. Then continuous ACQ values will be converted into binomial responses (1= an improvement of at least 0.5, 0= no improvement) and generalized estimating equation (GEE) method will be used to analyze the dataset. The GEE model will include terms for treatment, age (12 to 17 or  $\geq 18$  years), region, visit, and treatment-by-visit interaction as fixed effects, and Baseline ACQ-7, Baseline-by-visit interaction, FEV1 prior to inhalation and FEV1 within 15 to 30 min post inhalation of salbutamol/albuterol (components of SABA reversibility) as covariates.

The SAS procedure PROC GENMOD will be used.

Combining results from X copies of original dataset:

3. In the next step, results from each copy, obtained from GEE method will be combined for the inference using Rubin's rule. The SAS procedure PROC MIANALYZE will be used for combining the results considering the linear scale and then we will take exponential of combined result to obtain the odds ratio.

The estimated adjusted odds ratio will be displayed along with the associated 95% confidence interval and p-value (two-sided).

The proportion of patients who achieve an improvement of at least 0.5 at Week 12 in the change from baseline in AQLQ (i.e. increase of AQLQ score of at least 0.5 from baseline) will be analyzed using the same procedure as mentioned above for ACQ-7, with the following changes:

Replace ACQ-7 in all steps by AQLQ. Change step 1 as follows.

1. In Step 1, Impute missing covariates (baseline AQLQ, FEV1 prior to inhalation and FEV1 15 to 30 min post inhalation value) and missing continuous AQLQ values at Week 12 using the MI approach based on the fully conditional specification (FCS) method for 100 times and obtain 100 imputed datasets. Missing baseline AQLQ, FEV1 prior to inhalation and FEV1 15 to 30 min post inhalation value will be imputed separately for each treatment group using a model with age group, geographic region, and the respective other covariates (baseline AQLQ, FEV1 prior to inhalation and FEV1 15 to 30 min post inhalation value) as predictors. Missing Week 12 values will be imputed separately for each treatment group using a model with the imputed values of age group, geographic region, baseline AQLQ, FEV1 prior to inhalation, FEV1 15 to 30 min post inhalation.

- **Linear Mixed Model Analysis of Covariance (ANCOVA)**

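### The Week 12 imputation model for the ACQ-7 responder analysis lists baseline FEV1 where baseline ACQ-7 belongs

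*SAP*

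**What the plan says.** The proportion of patients whose ACQ-7 falls by 0.5 or more at Week 12 is one of the other secondary endpoints (SAP 1.2.3). SAP 2.7.2 and 6.6 handle missing scores by multiple imputation of the continuous ACQ-7, conversion to responder or non-responder, a GEE model, and pooling by Rubin's rule.

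Section 6.6 gives the imputation models in Step 1:

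- The covariates to be imputed are baseline ACQ-7 and the two FEV1 values from the reversibility test.
- Day 30 ACQ-7 is imputed from "the imputed values of age group, geographic region, baseline ACQ-7, FEV 1 prior to inhalation" and the post-inhalation value.
- Week 12 ACQ-7 is imputed from age group and "geographic region, baseline FEV 1 , FEV 1 prior to inhalation, FEV 1 15 to 30 min post inhalation, and Day 30 value as predictors".

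The GEE model in Step 2 has "region, visit, and treatment-by-visit interaction as fixed effects, and Baseline ACQ-7, Baseline-by-visit interaction" and the two reversibility values; baseline FEV1 is not in it. SAP 2.7.2 adds that "all the analyses described for ACQ-7 will be repeated for ACQ-5".

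**The concern.** Baseline ACQ-7 sets each patient's threshold for response. An imputation model that leaves it out assumes that, once Day 30 and the FEV1 values are known, baseline ACQ-7 says nothing more about Week 12. The analysis model makes no such assumption, so the two are uncongenial.

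If the assumption fails, patients with a low baseline are given Week 12 scores that are too high and are counted as responders too seldom. Patients with a high baseline are counted too often. At stake are the odds ratio, confidence interval and p-value for the Week 12 responder endpoint and for its ACQ-5 repeat. Protocol section 9 does not use off-treatment measurements for efficacy, so Week 12 scores of patients who stop treatment early are among those imputed.

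**Working it through.** **The text.** The plan gives no figure for this analysis, so the first check is to set the models side by side.

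| Place in the SAP | Baseline term used |
|---|---|
| 6.6, tipping point for trough FEV1, Week 12 step | baseline FEV1: "geographic region, baseline FEV 1 , FEV 1 prior to inhalation, FEV 1 15 to 30 min post inhalation, and Day 2 value as predictors" |
| 6.6, ACQ-7 responder, covariates to impute | baseline ACQ-7; baseline FEV1 not listed |
| 6.6, ACQ-7 responder, Day 30 step | baseline ACQ-7 |
| **6.6, ACQ-7 responder, Week 12 step** | **baseline FEV1; baseline ACQ-7 absent** |
| 6.6, ACQ-7 responder, GEE model | baseline ACQ-7 and its interaction with visit |
| 6.6, AQLQ responder, Week 12 step | own baseline: "geographic region, baseline AQLQ, FEV 1 prior to inhalation, FEV 1 15 to 30 min post inhalation" |
| 2.6.2, ACQ-7 MMRM | "will include Baseline ACQ-7 score instead of Baseline FEV 1" |

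The Week 12 list is the tipping-point list with one word changed. It also calls for an imputed baseline FEV1 that Step 1 never produces. Section 2.7.2 names no imputation predictors, and section 4 mentions only the addition of ACQ-5, so neither corrects it.

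**When bias arises.** With B, D and W for baseline, Day 30 and Week 12 ACQ-7, the standardised coefficient of baseline given Day 30 is (rBW - rBD × rDW) / (1 - rBD²). There is bias only if this differs from zero. The documents give no correlations, so three cases are assumed:

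- A: (0.30 - 0.46 × 0.65) / (1 - 0.46²) = 0.00
- B: (0.45 - 0.50 × 0.65) / (1 - 0.50²) = 0.17
- C: (0.60 - 0.60 × 0.60) / (1 - 0.60²) = 0.38

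**Size, by simulation.**

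- From SAP section 3: 375 per arm, 10% missing at Week 12, SD 0.80, difference -0.18.
- Assumed: baseline ACQ-7 normal (mean 2.0, SD 0.65) truncated below at 1.5; Week 12 means 1.55 (MF) and 1.37 (QMF149); baseline FEV1 correlated -0.25 with baseline ACQ-7; half of those missing Week 12 also missing Day 30.
- Imputation by arm, then a logistic model for Week 12 response.

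Results with dropout unrelated to baseline; the middle columns are responder rates among imputed patients:

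| Case | Baseline below 1.8: imputed vs true | Baseline above 2.4: imputed vs true | Odds ratio: imputed vs true |
|---|---|---|---|
| A | 49.3% vs 49.5% | 75.8% vs 76.0% | no bias |
| B | 50.5% vs 56.6% | 75.5% vs 72.5% | 1.50 vs 1.50 |
| C | 52.7% vs 66.7% | 74.3% vs 68.0% | 1.58 vs 1.60 |

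Whole-arm responder rates move by at most 0.4 points. If both arms lose mainly high-baseline patients, the odds ratio still moves by less than 1% (B and C).

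Only dropout that depends on baseline in opposite directions by arm (log-odds slope 1 per SD) moves it further. If MF loses high-baseline and QMF149 low-baseline patients, it goes from 1.50 to 1.45 (B) and 1.58 to 1.47 (C). The reverse gives 1.50 to 1.55 and 1.58 to 1.68.

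ACQ-7 item 7 is FEV1 % predicted, so the FEV1 terms carry some information on baseline ACQ-7. Raising that correlation to -0.5 does not remove the low-baseline error: 51.7% vs 58.6% (B) and 54.7% vs 67.1% (C).

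**Second simulation.** Different assumptions were used: baseline mean 2.3, SD 0.5; five sets of correlations; no FEV1 terms. Among imputed patients the error was -4.6 to -13.7 points at baseline below 2 and +2.2 to +8.1 at 2.5 or above. Over all imputed patients it was at most 3.1 points, which at 10% missing is 0.10 × 3.1 = 0.3 points for a whole arm. The largest odds-ratio change was 1.527 to 1.513.

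In both simulations, adding baseline ACQ-7 brought the band rates to within about 1 point of the truth.

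**The case against.** The text error is not in dispute. The case against giving it weight is about size.

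- **The reported estimate hardly moves.** With 375 per arm and response of about 60% and 69%, the standard error of the log odds ratio is √(1/(375 × 0.60 × 0.40) + 1/(375 × 0.69 × 0.31)) ≈ 0.15. The case C shift is ln(1.60/1.58) = 0.013, under a tenth of that. This stands.
- **Response by baseline ACQ-7 band is not a planned output.** SAP 2.2.1 uses those bands only for trough FEV1. This stands: the band errors show the mechanism, not a result that will be reported.
- **The larger shifts need a contrived dropout pattern.** Even then ln(1.58/1.47) = 0.07 is about half a standard error. Nothing in the documents points to that pattern, so it marks an outer limit only.
- **The simulations simplify.** They use a Week 12 logistic model instead of the two-visit GEE, the first with 10 imputations instead of 100, and the correlations are assumed. This limits confidence in the exact sizes, not in the direction.
- **Baseline FEV1 might be a deliberate auxiliary variable.** This is weak, because Step 1 does not impute it. It would not explain leaving out baseline ACQ-7 either.
- **The code may already be right.** SAP 6.6 places it in the TFL shells, which are not available here. If so, the SAP text still needs to agree with it.

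**Conclusion.** The concern holds. As written, the SAP specifies the wrong imputation model for a listed secondary endpoint, in conflict with its own Day 30 step, GEE model, AQLQ version and ACQ-7 MMRM. That conclusion rests on the text alone and is firm.

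The bias is conditional. It is nil if baseline ACQ-7 adds nothing beyond Day 30 and the FEV1 values. Otherwise, under the assumed correlations, it is several points in opposite directions at the two ends of baseline severity, among the 10% or so of patients imputed. The odds ratio changes by about 1% or less unless dropout runs in opposite directions by arm.

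The primary trough FEV1 analysis and the ACQ-7 MMRM do not use this step. The test hierarchy stops at the key secondary endpoint ("the key secondary endpoint ACQ-7 will be tested only if the primary endpoint" is significant), so no confirmatory claim depends on it. It should be corrected because a programmer following the SAP would fit the wrong model, and one who silently corrected it would depart from the SAP.

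**What to change.** In SAP 6.6, Logistic regression analysis, Step 1, replace baseline FEV1 with baseline ACQ-7 in the Week 12 imputation model, and state that the ACQ-5 repeat uses baseline ACQ-5. Keep the Day 30 value and the two reversibility FEV1 values. If baseline FEV1 is wanted as an auxiliary variable, keep it alongside baseline ACQ-7 and add it to the covariates imputed in Step 1. Check that the PROC MI code in the TFL shells matches before database lock.

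The cost is one phrase in the SAP and one variable in the PROC MI call. No new data are needed.

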6.4.2 Asthma Control Questionnaire (ACQ-7)

In this study, the ACQ-7 (Appendix 5) will be used to assess improvements in asthma symptom control. The ACQ-7 (Juniper et al 1999; Juniper et al 2005, and Juniper et al 2006) is a seven-item disease-specific instrument developed and validated to assess asthma control in patients in clinical trials as well as in individuals in clinical practice. ACQ-7 will be provided to the site. All seven items are then scored on a 7-point Likert scale, with 0 indicating total control and 6 indicating no control. The questions are equally weighted and the total score is the mean of the seven items.

The proportion of patients who achieve an improvement of at least 0.5 in ACQ-7 (i.e., decrease of ACQ-7 score of at least 0.5 from Baseline) at post-baseline visits will also be analyzed.

The first 6 questions of the ACQ-7 are to be completed by the patient while the last question (question 7) is to be completed by the study investigator using spirometry data generated by the spirometry equipment. The ACQ-7 should be completed at the study site at Visits 101, 102, 202, 204 and TD Visit if applicable.

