6.4.3 Asthma Quality of Life Questionnaire (AQLQ-S +12)

The AQLQ-S +12 is a 32-item disease specific questionnaire designed to measure functional impairments that are most important to patients with asthma (Appendix 6). It consists of 4 domains: symptoms, emotions, exposure to environmental stimuli and activity limitation. Patients are asked to recall their experiences during the previous 2 weeks and to score each item on a 7-point scale. The overall AQLQ score is the mean response to all 32 questions (Juniper et al 1992, and Juniper et al 1993). Clinically important differences in scores between any two assessments have been determined by the authors of the AQLQ. Changes in scores of 0.5 are considered clinically meaningful; changes of 1.0 are considered as moderate and > 1.5 as large changes for any individual domain or for the overall summary score (Juniper et al 1994).

AQLQ should be completed at Visits 102 and 204.

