### 2.7.7 Quality of life as assessed by Asthma Quality of Life Questionnaire (AQLQ-S+12)

AQLQ is a 32-item disease specific questionnaire designed to measure functional impairments that are most important to patients with asthma, with a recall time of two weeks and each question to be answered on a 7-point scale (1-totally limited/problems all the time, 7-not at all limited/no problems). It consists of 4 domains:

- Symptoms = Mean of Items 6, 8, 10, 12, 14, 16, 18, 20, 22, 24, 29, 30 (12 items)
- Activity limitation = Mean of Items 1, 2, 3, 4, 5, 11, 19, 25, 28, 31, 32 (11 items)
- Emotional function = Mean of Items 7, 13, 15, 21, 27 (5 items)
- Environmental stimuli = Mean of Items 9, 17, 23, 26 (4 items)
- Overall Score = Mean of Items 1 to 32 (32 items)

[name], developer of AQLQ questionnaire suggests no more than 10% of missing data. This means that for a questionnaire of 32 items, no more than 3 items should be missing. Further, for the activity and symptom domains, the recommendation is no more than 1 missing value per domain, and for the emotional function and environmental stimuli domains, no missing responses at all. Missing individual items will be imputed similarly to missing items for ACQ-7.

For the overall score and each respective domain score measured at Week 12, treatment group comparison will be performed using the same ANCOVA model as specified for rescue medication use with baseline AQLQ as covariate.

The proportion of patients who achieve an improvement of at least 0.5 at Week 12 in the change from baseline in AQLQ (i.e. an increase of AQLQ score of at least 0.5 from baseline) will be analyzed using a logistic regression model via GEE on the FAS as specified for ACQ-7 analysis except that the GEE model will include terms for treatment, age (12 to 17 or  $\geq 18$  years), region as fixed effects, and baseline AQLQ, FEV1 prior to inhalation and FEV1 within 15 to 30 min post inhalation of salbutamol/albuterol (components of SABA reversibility) as covariates. The handling of missing data will also be the same as for ACQ-7, i.e., first missing continuous AQLQ values will be imputed using a MI method under MAR assumption. Then continuous AQLQ values will be converted into binomial responses and GEE method will be used to analyze the datasets and then the results from GEE method will be combined for the inference.

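### The imputation of missing Week 12 AQLQ uses no on-treatment information; adding scheduled Day 30 ACQ-7 would be a low-priority, nearly free improvement

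*SAP*

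**What the plan says.** SAP 2.7.7 plans a responder analysis of AQLQ (gain of at least 0.5 at Week 12). For this analysis "first missing continuous AQLQ values will be imputed using a MI method under MAR assumption"; the scores are then dichotomised and analysed by logistic regression via GEE. The model has treatment, age group, "region as fixed effects, and baseline AQLQ" and the FEV1 values before and after salbutamol/albuterol.

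The imputation is set out in SAP 6.6, in the AQLQ version of Step 1:

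- "Missing Week 12 values will be imputed separately for each treatment group". As for the predictors, the SAP does this "using a model with the imputed values of age group, geographic region, baseline AQLQ" and the same two FEV1 values. This is done "for 100 times and obtain 100 imputed datasets".
- The step also fills in missing covariates: "In Step 1, Impute missing covariates (baseline AQLQ" and the two FEV1 values).

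On data collection, Protocol 6.4.3 says "AQLQ should be completed at Visits 102 and 204". Protocol 6.4.2 says "The ACQ-7 should be completed at the study site at Visits 101, 102, 202, 204 and TD Visit if applicable". Protocol Tables 5-4 and 6-1 list no AQLQ at the treatment discontinuation visit. SAP 2.6.1 schedules ACQ-7 at Day 30, which is Visit 202.

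Elsewhere in SAP 6.6, missing Week 12 trough FEV1 is imputed with the Day 2 value among the predictors, and missing Week 12 ACQ-7 with the Day 30 value.

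**The concern.** The imputation model contains nothing that the responder model lacks. A patient who leaves after a poor Day 30 assessment is imputed like a completer with the same baseline. The missing-at-random assumption must therefore hold given baseline alone, although an on-treatment measure of asthma control exists for many of these patients.

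Some missing AQLQ is likely to follow poor control. Protocol 5.6.2 requires study treatment to stop after a severe exacerbation or a confirmed FEV1 fall of more than 50%. Table 5-4 then replaces scheduled visits by telephone contacts without AQLQ, and Protocol Section 9 bars off-treatment measurements from efficacy. The tipping-point analysis covers trough FEV1 only, so no planned analysis would show whether the AQLQ result is sensitive to this.

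At stake are the responder percentages and, if the link between control and dropout differs by arm, the treatment odds ratio.

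**Working it through.** **Plan's own figures.** The documents give no figure for the AQLQ responder analysis. Their 10% dropout and 375 per arm set the scale. With 338 per arm and two-sided 0.05, power is 0.928 for trough FEV1 (100 mL, SD 380 mL) and 0.833 for ACQ-7 (0.18, SD 0.80). The product is 0.928 × 0.833 = 0.773, which matches the stated 93% and 77%. Neither depends on this point.

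**Reasoning.** Let Y be Week 12 AQLQ, X the five baseline variables and A Day 30 ACQ-7. The plan draws missing Y from the completers' fit of Y on X within arm. Patients missing only Y add no information on Y given X, so the responder model returns the complete-case answer plus simulation noise. If dropout depends on A, dropouts and completers with equal X differ in Y, and both methods miss this. Drawing Y given X and A corrects it where A is observed.

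**Simulation.** By-arm normal imputation, dichotomised at +0.5, logistic model with robust standard error, Rubin's rule. Assumptions not in the documents: residual correlation of A with Y, AQLQ means and SDs, a true odds ratio of about 1.36, the dropout mechanism, and the share of dropouts with a Day 30 value.

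Log odds ratios with 750 patients, 100 trials, 20 imputations, 70% of dropouts with a Day 30 value:

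| Dropout driven by | Correlation | Missing | Full data | Complete case | Planned | Day 30 ACQ-7 added |
|---|---|---|---|---|---|---|
| Chance | 0.6 | 10% | 0.320 | 0.323 | 0.325 | 0.323 |
| Baseline | 0.6 | 10% | 0.308 | 0.311 | 0.308 | 0.305 |
| Day 30 control, MF only | 0.4 | 10% | 0.303 | 0.201 | 0.202 | 0.276 |
| Day 30 control, MF only | 0.6 | 10% | 0.304 | 0.143 | 0.143 | 0.260 |
| Day 30 control, MF only | 0.6 | 15% | 0.307 | 0.088 | 0.087 | 0.255 |

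- *Planned against complete case:* mean difference at most 0.003 and correlation 0.992 to 0.996 across rows. Under chance dropout the standard errors are 0.1712 and 0.1714. The difference within a single trial has an SD of 0.017 to 0.025, so the two agree closely but not digit for digit.
- *MF-only row at correlation 0.6, 10% missing:* exp(0.304) = 1.36 with full data, exp(0.143) = 1.15 as planned, exp(0.260) = 1.30 with Day 30 ACQ-7. Share of bias removed: (0.260 − 0.143)/(0.304 − 0.143) = 73%. Root mean square error against full data falls from 0.172 to 0.068.
- *Same scenario, 300,000 patients, 60% of dropouts with a Day 30 value:* (0.2439 − 0.1429)/(0.3039 − 0.1429) = 63% removed.
- *Equal link in both arms, 300,000 patients, correlation 0.4 to 0.7:* the planned log odds ratio falls short of full data by 0.007 to 0.016 (for example 0.3067 − 0.2910 = 0.016).
- *Equal link, a separate set of 150 trials of 375 per arm, correlation 0.6:* odds ratio 1.34 against 1.36. Responder rates are 57.1% and 63.5% against true 54.9% and 61.7%, so 2.2 and 1.8 points too high.
- *Gain when dropout is by chance:* standard error 0.170 with Day 30 ACQ-7 against 0.171 as planned.

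**The case against.** The strongest reply is that missing at random given baseline is a legitimate, stated assumption, that auxiliary variables are a refinement, and that this analysis lies outside the testing hierarchy with no power claimed. All of that stands, and it sets the priority.

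A reader might also infer more than the documents support:

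- *That the imputation does nothing.* Step 1 also imputes missing baseline AQLQ and FEV1 covariates, so it keeps patients whom a complete-case fit would drop. The equivalence holds for patients missing only the outcome.
- *That the odds ratio is biased.* A material shift needs a link between control and dropout that differs by arm. The documents neither state nor exclude one. In the MF-only scenario the error understates QMF149, so it would not create a false claim of benefit. The mirror case was not simulated and should act in the opposite direction.
- *That Day 30 ACQ-7 fully repairs the result.* Patients who leave before Day 30 have no such value, and the simulation favours the fix by driving dropout from the variable that is added.
- *That the two questionnaires measure the same thing.* ACQ-7 covers symptoms, rescue use and FEV1 with one-week recall. AQLQ covers functional impairment, including emotions and environmental exposure, over two weeks. The documents give no correlation.
- *That all later ACQ-7 values should be used.* By default SAP 6.3 keeps discontinuation-visit and unscheduled efficacy data out of imputation, and Day 84 ACQ-7 is collected at the same visit as AQLQ, so it is usually missing too.

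One further objection has some force. The continuous AQLQ analysis follows the rescue-medication ANCOVA, which does no imputation. Changing only the responder analysis puts the two on different missing-data assumptions.

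**Conclusion.** The point holds as a low-priority improvement to a secondary analysis. The planned imputation adds essentially nothing for patients missing only Week 12 AQLQ, and it leaves out an on-treatment predictor of the kind that the SAP uses for its two parallel imputations.

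The likely size runs from negligible (chance or baseline-driven dropout), through about 2 points on responder percentages and 0.01 to 0.02 on the log odds ratio (equal link), to an odds ratio of about 1.15 instead of 1.36 (MF-only link, correlation 0.6). At correlation 0.4 the MF-only figures are exp(0.202) = 1.22 against exp(0.303) = 1.35. These rest on the assumed inputs listed above. Adding Day 30 ACQ-7 was never materially worse in any scenario run. The primary and key secondary analyses, type I error control, sample size and power are untouched.

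**What to change.** In SAP 6.6, AQLQ Step 1, add ACQ-7 from the scheduled on-treatment Day 30 visit as an auxiliary predictor in the fully conditional specification model for Week 12 AQLQ, and impute it within the same model where it is missing. State that ACQ-7 from the discontinuation visit is not used, in line with SAP 6.3 and Protocol Section 9. Leave the GEE model as it is.

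Scheduled Day 84 ACQ-7 may be added. It helps only when AQLQ alone is missing, for instance when too many of its items are unanswered.

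The cost is one extra variable in one PROC MI call, with no new data. A sentence in SAP 2.7.7 should note that the responder analysis then conditions on Day 30 control while the continuous AQLQ ANCOVA does not.
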